# **1.3.** Schedule of Activities (SoA)

Study Period	Screening a		Days 1 to 60 Day 61 through Day 360													
Visit Number	V1	V2	V3	V4 b	V5 b	V6 b	V7 b	TC1	V8	V9	V10	V11	V12	V13	TC2	Early
Day Number	(up to 28 days)	D1	D2	D3	D4	D5	D6	D14	D30	D60	D90	D180	D270	D360	D367 d	Disce
Visit Windows	-	-	-	-	-	-	-	$\pm 3d$	$\pm 3d$	$\pm 3d$	$\pm 7d$	$\pm 7d$	$\pm 7d$	$\pm 7d$	V13 + 7d (+ 7d)	-
Informed consent	X															
Inclusion and exclusion criteria	Xe	Х														
Demography	X															
Physical examination	X								Х					Xf		Х
Medical history	Х															
Urine pregnancy test (for women of childbearing potential) e.g	X	X														
Laboratory assessments e,h	Х	Х					Х		Х	Xi	Xi			Xi		Х
Sample collection for biomarker assessment e		Х	Х	Х	Х											
12-lead ECG j	Х	Х	Х	Х	Х	Х	Х		Х	Xk	Xk	Xk	Xk	Xk		Х
ECG patch		Х	Х	Х	Х	Х	Х	Х	$X^{l}$	X m	Х					
Vital signs e,n	Х	Х	Х	Х	Х	Х	Х		Х	Х	Х	Х	Х	Х		Х
Height	Х															
Body weight and abdominal circumference	Х													Х		Х
Dispense AF symptom diary and train participant on proper use o	Х															
AF symptom diary review o		Х	Х	Х	Х	Х	Х	Х	Х	Х	Х	Х	Х	Х	Х	Х
Randomization		Х														
Study intervention p		Х														
Assessment of fat pads and injection procedure		Х														
AE/SAE review q	X	Х	Х	Х	Х	Х	Х	X	X	Х	Х	Х	Х	Х	Х	Х
PFT r	X								Х							
Concomitant medication and concurrent procedure review e	Х	X	X	Х	X	Х	х	x	Х	Х	X	X	Х	Х	Х	X

#### Protocol 1925-201-008 Amendment 1

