#### CONFIDENTIAL

#### AGN-151607

Study Period	Screening a				D	ays 1 to	60					Day 61	through l	Day 360		
Visit Number	V1	V2	V3	V4 b	V5 b	V6 b	V7 b	TC1	V8	V9	V10	V11	V12	V13	TC2	Early
Day Number	(up to 28 days)	D1	D2	D3	D4	D5	D6	D14	D30	D60	D90	D180	D270	D360	D367 d	Disc e
Visit Windows	-	-	-	-	-	-	-	$\pm 3d$	$\pm 3d$	$\pm 3d$	$\pm 7d$	$\pm 7d$	$\pm 7d$	$\pm 7d$	V13 + 7d (+ 7d)	-
AFEQT	Х								Х		Х	Х				Xs
AFSS	Х								Х		Х	Х				Xs
DASI	Х								Х		Х	Х				Xs
EuroSCORE IIt	Х															
SF-12v2	Х								Х		Х	Х				Xs
EQ-5D-5L	Х								Х		Х	Х				Xs
Record discharge from ICU		Х	Х	Х	Х	Х	Х									
Record discharge from hospital			Х	Х	Х	Х	Х									
Record any additional healthcare resource utilization								Х	Х	Х	Х	Х	Х	Х	X	Х
Serum sampling for immunogenicity assessment u	X								Х		Х					

AE = adverse event; AF = atrial fibrillation; AFEQT = Atrial Fibrillation Effect on Quality-of-life Questionnaire; AFSS = University of Toronto Atrial Fibrillation Severity Scale; D(d) = day; DASI = Duke Activity Status Index; Disc = discontinuation; ECG = electrocardiogram; EQ-5D-5L = A measure of health-related quality of life developed by the EuroQol Group; FU = follow-up; ICU = intensive care unit; PFT = pulmonary function test; SAE = serious adverse event; SF-12v2 = Short Form-12 Health Survey, version 2; TC = telephone call; V = visit

a Screening and randomization activities can occur on the same day. If screening and randomization occur on the same day, all assessments for Visit 1 and Visit 2 should be completed. Duplicate assessments (eg, laboratory assessments) do not have to be completed twice; please note a 12-lead ECG is required both before and after surgery.

b These visits are optional and are only required if the participant is still hospitalized. Participants may remain in the hospital beyond Day 6, based on the recovery from surgery. The study visit procedures will have to be performed each day until discharge.

c In case of early discontinuation, attempts will be made to follow-up with the participant.

d Day 367 must be at least 7 days and should be no more than 14 days after Visit 13 (Day 360).

e On Day 1, assessments to be performed prior to surgery.

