f Physical examinations should be conducted where feasible. If the participant cannot attend the study visit, then the physical examination can be omitted, after sponsor approval. g Local urine testing will be standard for the protocol unless serum testing is required by local regulation or IRB/IEC.

h Laboratory assessments (hematology, chemistry, coagulation and urinalysis) to be performed at screening, Day 1 and day of discharge. The day of discharge can be from Day 3 onwards.

i Laboratory assessments should be conducted where feasible. If the participant cannot attend the study visit and/or an in-home assessment is not feasible, then the laboratory assessments can be omitted, after sponsor approval.

j On Visit 2, Day 1, two 12-lead ECGs will be performed; 1 before surgery and 1 after surgery. PFT should be performed at a reasonable time apart from vital signs and ECG to avoid confounding ECG and vital signs data.

k 12-lead ECGs should be conducted where feasible. If the participant cannot attend the study visit and/or an in-home assessment is not feasible, then the 12-lead ECG can be omitted, after sponsor approval.

ECG patch must be worn for a full 30 days post-surgery, even if Day 30 visit occurs prior to Day 30 due to window allowance.

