11.2 Clinical Laboratory Parameters

Descriptive statistics for clinical laboratory values (in SI units) and changes from the baseline values at each assessment time point will be presented by visit and treatment group for all continuous laboratory parameters. Categorical laboratory parameters will be presented in listings. The laboratory parameters are:

Hematology: Basophils absolute cell count, eosinophils absolute cell count, hematocrit, hemoglobin, lymphocytes absolute cell count, monocytes absolute cell count, neutrophil absolute cell count, mean corpuscular hemoglobin (MCH), mean corpuscular hemoglobin concentration (MCHC), mean corpuscular volume (MCV), platelet count, percentage reticulocytes, red blood cell (RBC) count, and white blood cell (WBC) count.

Chemistry:	Albumin, alanine aminotransferase (ALT), alkaline phosphatase, aspartate aminotransferase (AST), direct bilirubin, indirect bilirubin, total bilirubin, blood urea nitrogen (BUN), calcium, chloride, total cholesterol, creatinine, estimated glomerular filtration rate (eGFR), glucose non-fasting, triglycerides, HDL, LDL, Hemoglobin A1c, potassium, total protein, and sodium.
Urinalysis:	Bilirubin, blood, glucose, ketones, leukocyte esterase, nitrite, pH, protein, specific gravity, urobilinogen, and microscopic examination (if blood or protein is abnormal)
Coagulation:	Prothrombin time (PT), activated partial thromboplastin time (aPTT), and thrombin time (TT).

Clinical laboratory test values will be considered potentially clinically significant (PCS) if they meet either the lower-limit or higher-limit PCS criteria listed in Table 11–2. The number and percentage of participants who have PCS postbaseline clinical laboratory values will be tabulated by treatment group at each assessment. The percentages will be calculated relative to the number of participants with available non-PCS baseline values and at least 1 postbaseline assessment. The numerator will be the total number of participants with available non-PCS baseline values and at least 1 PCS postbaseline value. A supportive listing of participants with PCS postbaseline values will be provided, including the PID number, baseline and all postbaseline (including non-PCS) values.

Shift tables from baseline to each post-baseline visit for clinical laboratory parameters will be presented by treatment group for the following categories: low, normal, and high, which are provided by lab vendor.

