15.0 Data Handling Conventions

15.1 Visit Time Windows

Table 15–1 presents the visits assigned for safety analyses and the corresponding range of treatment days (window) during which an actual visit may occur. Unless otherwise specified, efficacy parameters collected by visit (e.g., Quality of Life Outcomes) will use the same windows during which an actual visit may occur. All analyzable ePatch data collected from ePatches with a start date within the visit window will be included in the analysis for the derived visit for Days 60, 90, 180, 270, and 360.

Scheduled Visit	Study Day ^a	Time Window (Study Day Range)
Baseline	1	1
Day 2	2	2
Day 3	3	3
Day 4	4	4
Day 5	5	5
Day 6	6	[6, 10]
Day 14	14	[11, 21]
Day 30	30	[22, 45]
Day 60	60	[46, 75]
Day 90	90	[76, 135]
Day 180	180	[136, 225]
Day 270	270	[226, 315]
Day 360	360	> 315 days

Table 15–1Analysis Visit Windows

a Relative to the date of the study treatment. Day 1 = the date of the study treatment.

If the assessment date (if the assessment date is unavailable, use visit date instead) is on or after the date of the study treatment, the study day is calculated by assessment date – date of the study treatment + 1. If the assessment date is before the date of the study treatment, the study day is calculated by assessment date – date of the study treatment. Therefore, a negative day indicates a day before the start of the study treatment.

If a subject has 2 or more visits within the same window, the last visit with a non-missing value will be used for analysis. All postbaseline assessments will be considered for PCS categorization. All assessments will be included in respective listings.

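### The one scheduled in-hospital post-operative laboratory sample is taken at discharge, but the SAP has no discharge visit, so by-visit tables split it by length of stay and the PCS (potentially clinically significant) rule gives no rate at a visit

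*SAP*

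**What the plan says.** **Schedule.** Protocol Section 1.3, footnote h (repeated under SAP Table 4–1), reads: "Laboratory assessments (hematology, chemistry, coagulation and urinalysis) to be performed at screening, Day 1 and day of discharge". It adds: "The day of discharge can be from Day 3 onwards". The Day 1 sample is pre-operative, because footnote e also applies to the laboratory row: "On Day 1, assessments to be performed prior to surgery". The Schedule of Activities (SoA) shows the in-hospital sample under Visit 7 (Day 6). Further laboratory assessments are marked at Days 30, 60, 90 and 360 and at early discontinuation.

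**Visit assignment.** SAP 15.1 says that Table 15–1 "presents the visits assigned for safety analyses and the corresponding range of treatment days (window) during which an actual visit may occur". Study day is computed from the assessment date. The table has no discharge row. If several values fall in one window, the last non-missing one is used.

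**Displays.** SAP 11.2 gives descriptive statistics and changes from baseline by visit, and shift tables for each postbaseline visit. For PCS values it says that "PCS postbaseline clinical laboratory values will be tabulated by treatment group at each assessment", with percentages "relative to the number of participants with available non-PCS baseline values and at least 1 postbaseline assessment". The numerator is participants with a non-PCS baseline and at least one PCS postbaseline value, with no visit restriction. Protocol 9.4.2.2 has the same combination.

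**The concern.** The discharge sample is the scheduled laboratory look at the acute period after injection; the next one is at Day 30. Two rules make it hard to read.

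First, its column depends on when the participant goes home. The Day 3 column can hold only the fastest recoveries, and the Day 14 column only long stays. Length of stay is an efficacy variable and a win-ratio component in SAP 10.3, and protocol 4.1.1 hypothesises a favourable effect on resource use. Each early column is thus conditioned on something that treatment may change. Arms could differ there without any laboratory effect, or a real effect could be broken up over several sparse columns.

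Second, the PCS rule asks for a table by assessment but supplies an any-time numerator and denominator. A programmer must choose an interpretation, and neither obvious choice gives the proportion with a PCS value among those tested at that visit.

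**Working it through.** The plan states no figure on this point, so there is none to reproduce.

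**Step 1. Where the discharge sample goes.** Footnote h set against Table 15–1 and the SoA laboratory row:

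| Study day of discharge | Analysis visit (window) | Laboratory mark in the SoA at that visit |
|---|---|---|
| 3 | Day 3 (single day) | none |
| 4 | Day 4 (single day) | none |
| 5 | Day 5 (single day) | none |
| 6 to 10 | Day 6 [6, 10] | yes, Visit 7 |
| 11 to 21 | Day 14 [11, 21] | none (telephone contact) |
| 22 to 45 | Day 30 [22, 45] | yes, Visit 8 |

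In the last row a later Day 30 sample replaces the discharge sample in the by-visit summaries under the last-value rule.

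**Step 2. Two readings of the PCS table.**
- Literal: numerator and denominator are both any-time, so every column repeats the same any-time percentage.
- Numerator limited to the visit, denominator as written: displayed % = PCS % among those sampled × share sampled in that window.

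**Step 3. Size of the dilution under the second reading.** Assumptions, none of them from the documents: PCS rate 20% at discharge whatever the day, all participants with a non-PCS baseline and exactly one discharge sample, and the discharge splits below. The 100 per arm comes from SAP 13.0.

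Worked cell (middle split, Day 6): 100 × 0.45 = 45 sampled; 45 × 0.20 = 9 with a PCS value; 9/100 = 9% displayed, against 9/45 = 20% among those tested.

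| Assumed split over Day 3/4/5/6/14 | Displayed PCS % |
|---|---|
| Middle: 5/15/25/45/10% | 1 / 3 / 5 / 9 / 2 |
| Shorter stays: 15/25/30/25/5% | 3 / 5 / 6 / 5 / 1 |
| Longer stays: 2/8/15/60/15% | 0.4 / 1.6 / 3 / 12 / 3 |

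A shorter-stay arm beside a longer-stay arm would show 5% against 12% at Day 6 with the same 20% risk. That contrast is deliberately wide. A milder shift, from the middle split to 8/22/30/33/7%, gives 1.6 / 4.4 / 6.0 / 6.6 / 1.4. Its largest gap is 9.0 − 6.6 = 2.4 points. With 100 per arm the standard error of that difference is √[(0.09 × 0.91 + 0.066 × 0.934)/100] = 3.8 points.

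**Step 4. Precision.** Even with the tested-at-visit denominator, splitting multiplies the standard error by 1/√share relative to one column holding everyone. For the middle split the factors are 4.5, 2.6, 2.0, 1.5 and 3.2. The denominator change alone also leaves each column selected by length of stay.

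**The case against.** The strongest reply is that little depends on these columns. SAP 11.2 is descriptive, with no test or decision rule. SAP 15.1 and 15.2 count every postbaseline value for PCS determination, so an any-time incidence compares the arms whatever window the discharge sample falls in. A listing shows all values for participants with a PCS result, protocol 8.2.4 sends clinically relevant laboratory changes to the AE page, and the DSMB reviews safety data. The table specifications are in a separate document and might settle the PCS wording. The sizes above rest on assumptions, and a mild shift in discharge days stays within one standard error. A pooled discharge visit would still mix post-operative days.

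Most of this stands and limits the point. It does not remove it: the rules as written still produce early by-visit, change-from-baseline and shift columns sorted by length of stay.

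A reader might infer more than the documents support:
- That this is the only scheduled post-operative sample. It is the only scheduled in-hospital one; Days 30, 60, 90, 360 and early discontinuation follow. Footnote b, which asks for visit procedures each day until discharge, may even imply repeat samples after Day 6.
- That the PCS denominator is simply wrong. It agrees with its numerator for an any-time incidence; it conflicts only with tabulation by assessment.
- That no laboratory column compares randomised groups. This applies to the early in-hospital columns, not to the later visits.
- That 12-lead ECG and vital signs share the problem. Both are also scheduled at Day 2, which is not optional, and SAP 11.3 and 11.4 do not tabulate PCS by assessment.

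**Conclusion.** The point holds within those limits and should be corrected. From the text alone, the discharge sample is split over five analysis visits, four of which have no laboratory mark in the SoA, with a tail into Day 30 where it can be dropped from the by-visit summaries. The early columns are conditioned on length of stay and do not compare the arms as randomised. The instruction to tabulate PCS by assessment is not matched by its numerator and denominator, so no column gives a PCS rate at a visit.

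The numerical size is illustrative only. It needs the assumed 20% rate, the assumed discharge splits and a visit-limited numerator that the SAP does not write. If nearly all participants left on Days 6 to 10, the scatter would be small. The mismatch in the PCS definition would remain for every by-visit laboratory row.

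**What to change.** 1. Add to SAP 15.1 a derived Discharge analysis visit for laboratory parameters: the sample on the day of index discharge or, if missing, the last in-hospital post-operative sample. Use it for the main by-visit, change-from-baseline, shift and PCS displays of the in-hospital period.
2. Summarise the study day of that sample by arm, because sampling time still varies with length of stay.
3. In SAP 11.2, define by-visit PCS as participants with a non-PCS baseline and a PCS value at that visit, divided by participants with a non-PCS baseline and any value at that visit. Keep the present any-time definition as an overall row.

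Hospital discharge is already recorded, so no new data are needed. The cost is SAP wording and a little programming. The drawback is that the Discharge visit pools different post-operative days, which is why item 2 belongs with it.

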11.3 Vital Signs

Descriptive statistics for vital signs (systolic and diastolic blood pressures, pulse rate, respiration rate, temperature, body weight, abdominal circumference, and body mass index) and changes from baseline values at each visit will be presented by treatment group.

Vital sign values will be considered PCS if they meet both the observed-value criteria and the change-from-baseline criteria listed in Table 11–3. The number and percentage of participants with PCS postbaseline values will be tabulated by treatment group. The percentages will be calculated relative to the number of participants with available baseline values and at least 1 postbaseline assessment. The numerator will be the total number of patients with available baseline values and at least 1 PCS postbaseline values. A supportive listing of participants with PCS postbaseline values will be provided, including the PID number, baseline and all postbaseline (including non-PCS) values.

	Elec	Elas Criteria^a		Criteria ^a
Parameter	Flag	Observed Value	Change From Baseline	
Sitting systolic blood	High	≥ 160	Increase of ≥ 20	
pressure, mm Hg	Low	≤ 9 0	Decrease of ≥ 20	
Sitting diastolic blood pressure, mm Hg	High	≥ 105	Increase of ≥ 15	
	Low	≤ 50	Decrease of ≥ 15	
Sitting pulse rate, bpm	High	≥110	Increase of ≥ 15	
	Low	≤ 5 0	Decrease of ≥ 15	
XX7 * 1 / 1	High		Increase of $\geq 7\%$	
weigni, kg	Low	_	Decrease of $\geq 7\%$	

 Table 11–3
 Criteria for Potentially Clinically Significant Vital Signs

a A postbaseline value is considered potentially clinically significant if it meets both the observed-value and the change-from-baseline criteria.

bpm = beats per minute.

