#### AGN-151607

m ECG patch must be used during the first 7 days following Day 60, Day 90, Day 180, Day 270 and Day 360 visits.

n Vital signs taken after a participant has been in a resting position for a minimum of 5 minutes; include blood pressure, pulse, respiration rate, and body temperature. On Visit 2, Day 1, vital signs will be measured before and after surgery.

• AF symptom diary must be used for first 30 days after surgery (or until early discontinuation if before Day 30) and during the first 7 days following Day 60, Day 90, Day 180, Day 270 and Day 360 visits. The diary should be returned to the site and be part of the medical records.

p Unblinded site pharmacist or designee will prepare drug; injected by investigator who is blinded to study intervention.

- q Method of detecting AEs and SAEs: care will be taken not to introduce bias when detecting AEs and/or SAEs. Open-ended and nonleading verbal questioning of the participant is the preferred method to inquire about AE occurrences.
- r Pulmonary function to be assessed using a spirometer and will include forced vital capacity (FVC) and the forced expiratory volume in 1 second (FEV1), 3 seconds (FEV3) and 6 seconds (FEV6). Note, if local policies contraindicate or prohibit PFT assessments due to potential for viral spread or microbial precautions, then the PFT is not required after explicit approval from the sponsor.

s If participant withdraws after Day 180, these early discontinuation procedures will not be performed.

t Impaired prognosis defined as EuroSCORE II > 7% perioperative mortality at screening is exclusionary.

u Serum collection should be conducted where feasible. If the participant cannot attend the study visit and/or an in-home assessment is not feasible, then the serum collection can be omitted, after sponsor approval.

AGN-151607

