### 4.1.1. Clinical Hypotheses

Injection of AGN-151607 into epicardial fat pads near the pulmonary veins and atria will prevent the occurrence of POAF, reduce the incidence of negative outcomes known to be associated with POAF, favorably impact health care resources utilization, and be well-tolerated and safe in patients undergoing open-chest cardiac surgery.

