11.4 Electrocardiogram

Descriptive statistics for ECG parameters (heart rate, RR interval, PR interval, QRS interval, QT interval, and QTc) and changes from baseline values at each assessment time point to the end of study will be presented by treatment group. The QTc will be calculated using both the Bazett and Fridericia corrections (if the vendor does not provide).

Electrocardiographic parameter values are considered PCS if they meet or exceed the higherlimit PCS criteria listed in Table 11–4. The number and percentage of participants with PCS postbaseline ECG values will be tabulated by treatment group. The percentages will be calculated relative to the number of participants with available baseline values and at least 1 postbaseline assessment. The numerator is the total number of participants with available baseline values and at least 1 PCS postbaseline value. A supportive listing of participants with PCS postbaseline values will be provided, including the PID number, baseline, all postbaseline (including non-PCS) values, and change from baseline.

Parameter	Unit	Higher Limit
QRS interval	msec	≥ 120
QRS interval	msec	>120 and increase from baseline > 25%
PR interval	msec	≥ 230
PR interval	msec	>230 and increase from baseline > 25%
QTc	msec	>480 or increase from baseline > 60
QTc	msec	increase from baseline > 30

 Table 11-4
 Criteria for Potentially Clinically Significant Electrocardiograms

QTc = QT interval corrected for heart rate.

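### The any-time PCS tables for vital signs and ECG give longer-staying participants more chances to be flagged, so a difference in stay between arms can shift the percentages without a drug effect

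*SAP*

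**What the plan says.** **When readings are taken.** The Protocol 1.3 Schedule of Activities marks vital signs and 12-lead ECG at Visits 2 to 7, then at Day 30, 60, 90, 180, 270 and 360. Its footnote on Visits 4 to 7 (Days 3 to 6) reads "These visits are optional and are only required if the participant is still hospitalized". For stays beyond Day 6 it adds "The study visit procedures will have to be performed each day until discharge", which Protocol 8 repeats. The laboratory footnote states "The day of discharge can be from Day 3 onwards". Everyone has a post-operative set on Day 1: for vital signs, "On Visit 2, Day 1, vital signs will be measured before and after surgery", and a second ECG is taken after surgery. The Day 14 contact is a telephone call with neither measurement.

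**How PCS is counted.** For vital signs (SAP 11.3): "The numerator will be the total number of patients with available baseline values and at least 1 PCS postbaseline values". For ECG (SAP 11.4): "The numerator is the total number of participants with available baseline values and at least 1 PCS postbaseline value". Both denominators are participants with a baseline and at least one postbaseline assessment. SAP 15.1 adds "All postbaseline assessments will be considered for PCS categorization", and SAP 15.2 brings in repeat and unscheduled values. By contrast, SAP 11.2 tabulates laboratory PCS at each assessment.

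**Means.** Changes from baseline are summarised by visit. The Day 6 window in SAP 15.1 covers Days 6 to 10, and the last non-missing value is used.

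**Stay as an outcome.** Protocol 2 links POAF to longer hospital stays. Protocol 4.1.1 expects the drug to "reduce the incidence of negative outcomes known to be associated with POAF". SAP 10.3 compares hospital and ICU stay between arms.

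**The concern.** An at-least-once count rises with the number of looks. Here the number of looks is set by discharge, which happens after treatment and may be affected by it. Nothing in SAP 11.3, 11.4, 15.1 or 15.2 adjusts for the number of readings or limits the count to visits that all participants share.

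The bias can run either way. If the drug shortens stay, its PCS percentages for pulse, blood pressure, PR, QRS and QTc fall for that reason alone, which could mask part of a real rate or conduction signal. If stays are longer on drug, part of an apparent signal would be spurious. Weight is unaffected, because it is scheduled only at screening, Day 360 and early discontinuation.

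The by-visit means have a related selection problem. The group measured shrinks from Day 3 onward as participants go home, and the Day 6 row takes its value from a later day for those who stay longest.

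**Working it through.** The plan states no PCS rate, stay difference or reading count, so there is no figure of its own to reproduce. The per-reading risk q and the stay differences below are assumptions. The reading counts and the 20-point POAF effect come from the documents.

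**Formula.** With the same q in both arms (no drug effect) and independent readings, P(at least one PCS in k readings) = 1 − (1 − q)^k.

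**Step 1: in-hospital readings only.** Compare one participant with 5 readings to the same participant with 2 or 5 more.

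| q | k = 5 | k = 7 | k = 10 | 7 minus 5 | 10 minus 5 |
|---|---|---|---|---|---|
| 3% | 14.1% | 19.2% | 26.3% | 5.1 | 12.1 |
| 5% | 22.6% | 30.2% | 40.1% | 7.5 | 17.5 |
| 10% | 41.0% | 52.2% | 65.1% | 11.2 | 24.2 |
| 15% | 55.6% | 67.9% | 80.3% | 12.3 | 24.7 |

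**Step 2: from a participant to an arm.** The documented route to a shorter stay is prevention of POAF. Protocol 9.2 plans for 47.8% on placebo and 27.8% on drug, so 47.8 − 27.8 = 20% of an arm would be spared POAF. Only that fifth changes its stay.
- If each case adds 2 days (assumed): 0.2 × (5.1 to 12.3) = 1.0 to 2.5 points.
- If each case adds 5 days (assumed): 0.2 × (12.1 to 24.7) = 2.4 to 4.9 points.

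The range is therefore about 1 to 5 points.

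**Step 3: whole-arm shift, counting later visits.** Eight sets are scheduled for everyone: Day 1 post-surgery and Days 2, 30, 60, 90, 180, 270 and 360. Each hospital day from Day 3 to discharge day L adds one, so k = 8 + (L − 2). That is 12, 13, 14 and 16 sets for discharge on Day 6, 7, 8 and 10.

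| q | Day 6 | Day 7 | Day 8 | Day 10 | Gap, Day 8 minus Day 6 |
|---|---|---|---|---|---|
| 1% | 11.4% | 12.2% | 13.1% | 14.9% | 1.8 |
| 2% | 21.5% | 23.1% | 24.6% | 27.6% | 3.1 |
| 5% | 46.0% | 48.7% | 51.2% | 56.0% | 5.3 |
| 10% | 71.8% | 74.6% | 77.1% | 81.5% | 5.4 |

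A 2-day shift of the whole arm gives about 2 to 5 points. If risk is concentrated in hospital (assumed 5% per in-hospital reading, 0.5% at each of the six later visits), P = 1 − 0.95^L × 0.995^6. That gives 28.7% for L = 6 and 35.6% for L = 8, a gap of about 7 points.

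**Step 4: correlation within a person.** With a beta-binomial model and an assumed correlation of 0.3, the 7-minus-5 gap in Step 1 falls from 5.1–12.3 to 1.6–5.4 points, before the factor of 0.2 is applied. With complete persistence the gap is zero.

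**Step 5: common visits only.** With k = 8 for everyone, equal q gives equal rates in both arms (7.7%, 14.9%, 33.7% and 57.0% at q = 1%, 2%, 5% and 10%). The artefact is then zero.

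**The case against.** **Size.** The strongest objection is that the likely artefact is small. A reader might take the 5-to-25-point gaps in Step 1 as differences between arms. They would be that only if every participant in one arm stayed 2 to 5 days longer. Through POAF prevention in 20% of participants, a 2-day difference in arm means needs 2 / 0.2 = 10 extra days per POAF case, and a 5-day difference needs 25. The documents support neither. With 100 per arm, the standard error of a difference in proportions is √(2 × 0.2 × 0.8 / 100) = 5.7 points at 20% and √(2 × 0.5 × 0.5 / 100) = 7.1 points at 50%, so the expected artefact is below the noise. This stands.

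**Inevitability.** A reader might also infer that the longer-staying arm must show more PCS events by construction. That needs both a stay difference and values that come and go. A persistent QRS of 120 msec or more is flagged at the first ECG whatever the stay. Nor does any abnormal value count: vital signs must meet both the observed-value and the change criterion.

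**Visibility.** The tables are descriptive with no planned test. Safety summaries already show the number of participants, PCS listings give all postbaseline values for flagged participants, and SAP 10.3 would reveal a stay difference. Cardiovascular events of interest and bradycardia are also tabulated as adverse events. It would therefore be too strong to say that a signal would be hidden.

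None of this equalises the number of readings. Arm percentages are how these parameters will be compared, and no summary of readings per participant by arm is planned.

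**Conclusion.** The dependence on length of stay is real and follows from the schedule and the counting rule together. It becomes a bias only if stay differs between arms and PCS values are not fully persistent. On the plan's 20-point POAF effect, with an assumed 2 to 5 hospital days per case and 3% to 15% risk per in-hospital reading, it is worth about 1 to 5 points, and less with within-person correlation or once later visits are counted. A whole-arm 2-day shift gives about 2 to 5 points at 1% to 10% risk per reading, or 7 if risk is concentrated in hospital. Day 3 to Day 6 means should be read as describing mainly inpatients, with selection growing toward Day 6. This is a modest problem of interpretation that merits a cheap improvement. It does not invalidate the safety analysis.

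**What to change.** - Keep the any-time PCS tables in SAP 11.3 and 11.4 unchanged.
- Add PCS for vital signs and ECG by visit with the number assessed, as SAP 11.2 does for laboratory values.
- Add a PCS count restricted to visits scheduled for everyone: post-surgery Day 1, Day 2, Day 30 and later visits where done.
- Report the number of assessments per participant by arm.
- Label Day 3 to Day 6 summaries as participants still hospitalized, with n and percent of the arm.

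The cost is SAP wording and a few extra tables from data already collected. The common-visit count should not be the sole comparison. It omits Days 3 to 6, whereas Protocol 4.1 places POAF usually at 2 to 5 days after surgery. It is also not perfectly common, because ECGs from Day 60 on may be omitted with sponsor approval and early leavers lack later visits. It must be read beside the any-time and by-visit tables.
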